# **Project Evaluation**

Four linked workstreams have been identified for programme evaluation that will together explore the research questions set out above. These are based on recommendations set out in the Treasury's Magenta Book. They include:

- Performance monitoring
- Economic modelling
- Process evaluation
- Impact evaluation

Rather than separate workstreams, these will be interlinked, for example with process and impact evaluation informing, providing inputs for and responding to the work on the economic model. This also means that modelling of the concepts used in different aspects of the work will take similar approaches. For example, as set out in the Economic Modelling section below, reflecting the low prevalence rate of most of the conditions individually, we will develop evidence both on individual conditions and on 'clusters' of conditions, grouping conditions with similar clinical characteristics, clinical pathways and natural histories together.

Genomics England will develop the performance dashboard and economic model internally, with input from external experts including health economists. As described above, process and impact evaluation will be delivered in partnership with an Evaluation Partner ensuring that the programmes of work are integrated, for example the impact evaluation feeding data to and responding to the requirements of the economic modelling work. Each of the evaluation workstreams are briefly discussed below.

#### Performance monitoring

A performance dashboard will be created to inform decision making and monitor programme delivery, consisting of a set of key performance indicators (KPIs) that are closely aligned with project ambition to inform decision making. This quantitative monitoring data will be collected through a variety of sources including:

- Data from Genomics England core systems
- Data fed back from the NHS as part of monitoring the programme.
- Data fed back to Genomics England by the partner performing the process and impact evaluations (see below)

Genomics England will develop the performance dashboard using appropriate software, such as Tableau. Where appropriate, data will be presented as a time series using data visualisation best

practice and updated regularly (live where possible). In some instances, further analysis or forecasting will be required to ensure the research questions are being answered.

Appropriate governance and accountability mechanisms will be established to monitor delivery, including uptake and results, and to remediate off-track KPIs. Monitoring will be ongoing throughout the programme.

## Economic modelling

GEL is developing an economic model internally for the health economic evaluation. The initial proposals for the model were produced through a collaboration between GEL and external experts, with the model itself developed by an external economic modelling team. GEL continues to liaise with the NSC and other expert teams on the model. We include a description of the model below, noting that it will be iterated and populated as data from the Generation Study and other studies are generated and responding to ongoing expert input and best practice.

The model aims to estimate the costs and benefits of genomic newborn screening alongside current newborn bloodspot screening. The model includes a control arm, current blood-spot test, as well as an intervention arm for the addition of genomic newborn screening. Consent rates for both screening tests are incorporated, resulting in a subset of babies receiving neither screening test.

The model takes a clustering approach, grouping conditions with similar clinical characteristics, clinical pathways and natural histories together. In total the model currently contains six clusters of conditions that have similar characteristics each of which is represented by around ten conditions. This subset of ~60 conditions, representing the 200+ conditions that will be screened for by WGS, was chosen based on prevalence, data availability, and also clinical importance. Within each cluster, condition-specific inputs are obtained for costs, utilities, and mortality rates, and a weighted cluster average is then calculated for each variable based on the relative prevalence of the condition within the cluster. The model is run individually for each of the six clusters and then aggregated to reach a population-level estimate, based on the relative prevalence of each cluster within the overall population. This allows for cost-effectiveness to be estimated both for individual clusters and for the overall group of conditions.

The model is structured in two phases. The first phase, a decision tree (shown below), considers the initial screening process and is used to define distinct groups of patients based on the outcome of screening. In the second phase, these groups of patients then progress through one of three distinct Markov models, each simulating a specific post-screening pathway. For the first phase, a weekly-cycle length is used to capture the costs associated with the screening tests, the sequencing process, the interpretation of the screening results and finally the cost of confirmatory diagnostic tests. In the second phase, an annual cycle length is applied to all Markov models, with a half-cycle correction implemented, to capture all the relevant costs and benefits that babies accrue as they are followed for a lifetime time horizon.

The first Markov model (Model A) tracks babies affected with a genetic disease but who have not been detected via WGS or blood-spot (false negative), or who were not detected because of non-participation in the screening programme (i.e., parents declined screening). The second Markov model (Model B) tracks babies with a genetic disease detected by WGS or blood-spot (apparent true positive). The third Markov model (Model C) tracks unaffected babies, this includes babies with

negative WGS or blood-spot results, babies with positive WGS or blood-spot results which was subsequently disproved as negative by a diagnostic test (apparent false positive), and finally unscreened babies that did not participate in either screening program and never develop a genetic condition (unaffected). The model includes the positive predictive value (PPV) and negative predictive value (NPV) for both the blood-spot and WGS screening tests, which determine the number of false negatives and false positives in the population.

Apparent true + Markov Model B Condition(s) Clinical pathway & orthogonal testing Genomic Newbor Apparent false Markov Model C Screening + Genetic Condition Markov Model A No condition suspected result orthogonal testing Markov Model C Apparent true Markov Model B Condition(s) Clinical pathway & suspected resul orthogonal testing Standard of Care Apparent false + Newborn Blood-spor - Genetic Conditi Markov Model A No condition suspected result orthogonal testing Genetic Condition Markov Model C Genetic Conditio Markov Model A

Markov Model C

Figure 9- Decision tree for the draft health economic model

Genetic Condition

Babies diagnosed with a genetic condition at birth, through either blood-spot or WGS will enter Markov model B in the "pre-symptomatic" health state, and those who subsequently receive treatment will continue through to the "asymptomatic-treatment" health state. From here, they will transition to one of three subsequent health states: "asymptomatic-complete response", "symptomatic-partial response", "symptomatic-treatment failure". The model also includes a "symptomatic-symptoms management" health state to reflect patients who will benefit from having a diagnosis, even without treatment initiation and those with uncertain condition status. Transition probabilities between health states are based on treatment efficacy rates, specific to each condition in the model. In addition, specific mortality rates are applied to each health state.

Babies diagnosed with a genetic condition at symptom onset, either due to false negative results or babies in the control arm who have conditions not screened for in the blood-spot test, will enter Markov model A. The health states in this model are similar to those in model B, except for the addition of a "symptomatic-diagnostic odyssey" health state, which captures the period of time between symptom-onset and receiving a diagnosis. In addition, in model A the "asymptomatic-treatment" state is replaced by the "symptomatic-treatment", since treatment will only begin after symptom onset and diagnosis. Despite the similarity in health-states between models A and B, the transition probabilities differ for some conditions due to reduced treatment efficacy when treatment

No Screen

is initiated at symptom onset rather than at birth. As with model B, specific mortality rates are applied to each health state.

Finally, Markov model C captures the progression of unaffected infants (false-positive, true-negative, and unaffected unscreened infants). Only two health states are considered for this model: "unaffected-well" and "death". For false positive patients, harms of a false diagnosis such as anxiety are captured within the first phase of the model, after a confirmatory negative test they are assumed to rejoin the "unaffected" population.

Specific costs and utilities are applied to each health state in the three Markov models, therefore patients accrue costs and quality-adjusted life years (QALYs) as they pass through the model. In terms of costs, the model considers treatment costs, direct medical costs, and direct non-medical costs (e.g., social care costs). Utility values for health states are adjusted to account for adverse events from treatments.

Initial data inputs in the model have been obtained from a wide range of sources. The majority of inputs have been sourced from published literature and publicly available datasets. In cases where there was a lack of data available, expert clinicians have been consulted to provide assumptions for the model. For healthcare resource use costs, an analysis of HES datasets has been conducted to obtain resource use inputs for each condition in the model. The model has been built to allow for live data from the Generation Study to be incorporated once available.

Discounting is applied in the model, and differential discount rates are used for costs and benefits. Costs are discounted at a rate of 3.5%, whereas benefits are discounted at a rate of 1.5%.

The key outputs of the model include costs, life years, and QALYs for the blood-spot and WGS arms of the model. These outputs are used to calculate an Incremental Cost Effectiveness Ratio (ICER) to evaluate the cost-effectiveness of introducing WGS screening for newborns. As well as overall costs, QALYs, and ICER estimates, the model also produces disaggregate ICERs for each of the six clusters of diseases in the model. This generates insights into the drivers of cost-effectiveness, particularly useful due to the large variation in treatment costs between the six disease categories.

The model also includes deterministic sensitivity analysis (DSA) to explore the effects of uncertainty on the model's results. As part of the DSA, model inputs are varied between their upper and lower bounds, resulting in a range of plausible results rather than single point estimates. Scenario analyses are also performed, for example on discount rates, to explore the effect of methodological uncertainty within the model.

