### Analytical approach

The NBSeq project studied the potential use of WES sequencing in a cohort of 1,728 children who had received a true or false positive result for an inherited metabolic condition as part of routine newborn screening. The exome-led approach had a specificity of 98.4% and a sensitivity of 88% compared to a specificity of 99.8% and a sensitivity of 99% for routine newborn screening. The authors concluded that it was not suitable as a first tier test for these conditions and highlighted the large number of false positives that this would yield if implemented as a second tier test. Of note, the analytical approach they used included variants of uncertain significance which would be expected to

tend towards lower specificity and positive predictive value than approaches proposed by more recent authors and favoured by studies currently in development.

A second study carried out by the BeginNGS study investigators looked at the performance of a proposed newborn sequencing pipeline focused on 388 genes by analysing whole genome data from 2,208 children who had undergone diagnostic whole genome analysis in the context of critical illness. The pipeline identified 108 of 119 (87%) diagnoses as well as 15 additional findings that were not identified on diagnostic testing. This corresponded to a sensitivity of 88.8%. This same pipeline was also applied to genome data from 457,707 UK Biobank participants (not expected to have a treatable childhood disorder) and was found to have a specificity of 99.7% following root cause analysis.

Prospective studies returning findings

There have only been three prospective studies of genomic newborn screening published that include return of findings to families.

The NC Nexus study used a WES-based approach to look for 466 childhood onset, treatable conditions in 45 children with an inherited metabolic disorder and 61 healthy newborns. The study also included randomisiation to be offered the option of receipt of results for a broader range of childhood conditions, adult onset treatable conditions and/or carrier status to inform reproductive choices. The study identified 5 of 28 children with deafness (18%), 15 of 17 children with inherited metabolic conditions as well as four children with treatable childhood conditions that would have been missed by routine newborn screening.

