The sample size calculation to estimate this incidence of genetic diseases was based on the normal approximation to the binomial distribution with simple random sampling assumed . For the sample size calculations the proportion of subjects screened positive was assumed to be 0.011, and it was derived from an estimate of the true population incidence, the middle point of the estimate, 1/572, by using the sensitivity of detection of 65% and specificity of detection of 99% . Dropout rate was assumed to be 10%. The sensitivity of detection of 65% and specificity of detection of 99% used in calculations is the lower bounds of the estimates obtained during bioinformatics prioritisation algorithm modelling. Expected specificity is discussed in more detail in Section 10. We note that sample size calculations for estimating prevalence in rare conditions are highly sensitive to the assumptions of test performance metrics, in particular the assumption on specificity . Therefore we will update the calculations before the study, when the list of conditions is finalised and sensitivity and specificity modelling for those conditions is complete, as well as monitor and update throughout the study. In addition, throughout the study we will be updating the calculations to monitor that the sample size is sufficient to evaluate expected study-wide true positive rate. See section 13 for more information.

To validate the sample size calculations further and to understand the behaviour of sample size in relation to other parameters, Monte Carlo simulations using a range of true population incidence, sensitivity and specificity were performed. An example of simulation, assuming 65% sensitivity, 99% specificity and 1/572 true incidence is depicted in Figure 5.

Figure 5 - An example of the Monte Carlo simulation of two-sided 95% confidence interval for the proportion of subjects screened positive assuming 99% specificity and 65% sensitivity. For each value in the sample size, the expected proportion of subjects screened positive was computed from a binomial distribution 15 000 times. The final confidence interval is obtained by clipping 95% of the values among the 15 000 (filled area). The dashed lines show the maximum and minimum values of the obtained proportion of subjects screened positive for each sample size. The dotted lines indicate the expected proportion of subjects screened positive +/- 6% error margin.

[figure not shown]

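### Cluster inputs weighted by prevalence alone fit the detected and missed babies they are applied to only if sensitivity is uniform within a cluster

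*Protocol*

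**What the plan says.** Section 13 (Economic modelling) groups conditions into six clusters and obtains costs, utilities and mortality by condition. It then pools them: "a weighted cluster average is then calculated for each variable based on the relative prevalence of the condition within the cluster". The unit of computation is the cluster: "The model is run individually for each of the six clusters and then aggregated to reach a population-level estimate".

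The decision tree sorts babies by screening result before these inputs are applied. "The second Markov model (Model B) tracks babies with a genetic disease detected by WGS or blood-spot (apparent true positive"). Model A takes affected babies who were missed or not screened. Control-arm babies whose condition lies outside the blood-spot test also go to Model A. Test performance enters as follows: "The model includes the positive predictive value (PPV) and negative predictive value (NPV) for both the blood-spot and WGS screening tests". The text does not say whether those values are set per test, per cluster or per condition.

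On treatment effect the section says: "Transition probabilities between health states are based on treatment efficacy rates, specific to each condition in the model". It does not say how these are pooled when the model runs at cluster level. Nowhere are the pooled inputs re-weighted for the chance of detection.

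**The concern.** A prevalence-weighted average describes all affected babies in a cluster. Model B does not hold all affected babies. It holds those a test found, and well-detected conditions are over-represented among them. The false negatives in Model A are the mirror image. One set of prevalence weights cannot describe both groups unless every condition in the cluster is detected equally well.

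The Protocol gives reasons to doubt that. Clusters are built on clinical likeness, pathway and natural course, not on detectability. Section 3 (Analytical approach, on challenges) ties sensitivity to knowledgebases that remain limited for many rare conditions. Section 10 (Analytical validity) assesses each gene separately and expects that sensitivity often cannot be measured directly. For blood-spot the difference is built in, because conditions it does not test for are never detected by it.

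At stake are the cluster ICERs and the overall ICER, which serve the secondary outcome on cost-effectiveness. More accurate condition-level inputs would not remove the mismatch, because it lies in the weights.

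**Working it through.** **Plan's own figure.** The Protocol reports no QALY, cost or ICER value, so there is none to reproduce.

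**Inputs.** The prevalence weights and the model structure come from Section 13. Mean sensitivity of 65% comes from Section 6 (Sample size), where it is called a lower bound. The splits of sensitivity within a cluster, the QALY gains of 2 and 8 and the equal prevalences are assumptions, because the Protocol gives none by condition. The whole gain is treated as prevalence-averaged, which is a further assumption because the pooling of transition probabilities is not stated.

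**Algebra.** For conditions in one cluster let w be the prevalence share, s the sensitivity, A and B the outcome in Models A and B, and d = B − A.

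- Prevalence weighting gives ΣwA + (Σws)(Σwd).
- The true detected and missed mixes give ΣwsB + Σw(1 − s)A = ΣwA + Σwsd.
- Error = (Σws)(Σwd) − Σwsd = −cov(s, d), per affected baby screened.

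The error is zero if s or d is constant or if they are uncorrelated. It is positive if the poorly detected conditions have the larger gain, and negative if they have the smaller. Replacing QALYs by costs gives the same result.

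**Two conditions, equal prevalence, mean sensitivity 0.65.** With gains of 2 and 8 (mean 5), prevalence weighting always credits 0.65 × 5 = 3.25.

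| Sensitivities | Gains | Correct value | Error |
|---|---|---|---|
| 0.65 / 0.65 | 2 / 8 | 0.5(0.65×2 + 0.65×8) = 3.25 | 0% |
| 0.90 / 0.40 | 5 / 5 | 0.5(0.90×5 + 0.40×5) = 3.25 | 0% |
| 0.75 / 0.55 | 2 / 8 | 0.5(0.75×2 + 0.55×8) = 2.95 | +10% |
| 0.75 / 0.55 | 8 / 2 | 0.5(0.75×8 + 0.55×2) = 3.55 | −8% |
| 0.90 / 0.40 | 2 / 8 | 0.5(0.90×2 + 0.40×8) = 2.50 | +30% |
| 0.90 / 0.40 | 8 / 2 | 0.5(0.90×8 + 0.40×2) = 4.00 | −19% |

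In the 0.90/0.40 rows the less detectable condition is 0.20/0.65 = 31% of detected babies and 0.30/0.35 = 86% of missed ones. It carries 50% of the weight in both models.

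**Blood-spot.** Assume a cluster in which 30% of prevalence is covered by blood-spot (detection 99%) and 70% is not (detection 0).

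- Every blood-spot detection is then a covered condition. With gain 2 for covered and 8 for uncovered conditions, each is credited 0.3×2 + 0.7×8 = 6.2 instead of 2 (+210%). With the gains swapped it is 0.3×8 + 0.7×2 = 3.8 instead of 8 (−53%).
- Blood-spot operates in both arms, so part of this cancels in the difference between arms. The extra WGS detections do not cancel. If practically all of them are uncovered conditions, each is credited 6.2 instead of 8 (6.2/8 − 1 = −22.5%) or 3.8 instead of 2 (3.8/2 − 1 = +90%). This arises even if WGS sensitivity is the same for every condition.

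**The case against.** The best defence has four parts.

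1. **The description is provisional.** The model is to be iterated, its tree is labelled a draft, live study data can be fed in, and sensitivity and scenario analyses are planned. This stands as mitigation and makes the change cheap. It does not answer the point. The weighting rule is stated, new data would pass through the same weights, and the sensitivity analysis is described as varying inputs, not weights.

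2. **Poor detection is limited by design.** Principle A in Section 4 requires reliable detection, and validity is checked for each gene. This narrows the spread of WGS sensitivity but does not make it uniform, since finding known variants reliably is not the same as finding an equal share of affected babies for each condition. It has no bearing on blood-spot coverage.

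3. **Similar conditions may have similar gains.** If so, the covariance is small and the assumed fourfold spread is too wide. This is possible, and it is why the figures are only illustrations. If PPV and NPV are cluster-specific, differences between clusters are also dealt with and only those within a cluster matter.

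4. **Transition probabilities are condition-specific.** Part of the benefit may therefore escape prevalence averaging. The Protocol does not say, so the size is uncertain.

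Two stronger readings are tempting. A reader might infer that genomic screening is being credited with benefits for conditions it mostly misses. The Protocol does not support this: no listed condition is given a sensitivity below one half, the overall 65% is a lower bound, and the error can run either way. A reader might also measure the error from the Background, where "The study identified 5 of 28 children with deafness (18%), 15 of 17 children with inherited metabolic conditions" suggests sensitivities of 18% and 88%. That contrast comes from another, exome-based study, and the two groups may well sit in different clusters, where this error does not arise.

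**Conclusion.** The point holds as a conditional one. The stated weights are correct for detected babies and for false negatives only under uniform sensitivity within each cluster. The Protocol neither states that assumption nor makes it plausible. For blood-spot it fails in any cluster that mixes covered and uncovered conditions, though cluster membership is not given.

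The direction is unknown: the ICER may be overstated, understated or unaffected. For WGS, plausible sizes run from 0% to about +10% or −8% under a modest sensitivity split, and about +30% or −19% under a wide one. These rest on assumed splits, equal prevalences and gains of 2 and 8 QALYs around a mean sensitivity of 65%. The blood-spot figures rest on an assumed 30% coverage and are larger.

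The primary outcome is not affected. The weights should be changed before any ICER is reported.

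**What to change.** - Weight Model B inputs by prevalence × sensitivity and Model A false-negative inputs by prevalence × (1 − sensitivity), separately for blood-spot and WGS. Set blood-spot sensitivity to zero for conditions it does not cover. Alternatively, run the decision tree by condition and aggregate to clusters afterwards, which gives the right mix automatically.
- Keep prevalence weights for babies who had neither test.
- State how condition-specific transition probabilities are pooled, and apply the same weights to them.
- Where WGS sensitivity for a condition cannot be measured, carry it as a range in the sensitivity analysis. Treat gene callability as an upper guide only, because it reflects detectability of known variants and not the share of affected babies who carry one. Update with the study's detections and false negatives.

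The cost is a change of weights in a model still under development. The downside is that condition-level WGS sensitivity is uncertain, so the reported ICER range will widen.

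### Annual cycles in the Markov phase of the economic model cannot represent a mean diagnostic delay much below six months, and they coarsen treatment start in screened babies as well

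*Protocol*

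**What the plan says.** All of this stands in Protocol Section 13, Economic modelling, unless another place is named.

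- The decision tree comes first: "For the first phase, a weekly-cycle length is used to capture the costs associated with the screening tests", and also those of sequencing, interpretation and confirmatory testing.
- The Markov phase follows: "In the second phase, an annual cycle length is applied to all Markov models, with a half-cycle correction implemented". It runs over a lifetime.
- Model A takes affected children who are diagnosed at symptom onset. It has a diagnostic-odyssey state, "which captures the period of time between symptom-onset and receiving a diagnosis".
- Model B takes screen-detected babies. They enter as pre-symptomatic and, if treated, move to the asymptomatic-treatment state.
- On how results accrue: "Specific costs and utilities are applied to each health state in the three Markov models". Each state in Models A and B also has its own mortality rate.
- Early treatment has a second route to benefit: between A and B "the transition probabilities differ for some conditions due to reduced treatment efficacy when treatment" starts at symptom onset and not at birth.

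No shorter early cycle, tunnel state or cycle-length scenario is described. The model is presented as one that will be iterated.

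**The concern.** Time spent in a state determines the cost and QALYs charged to it. In Model A the time in question is the wait for a diagnosis. In Model B it is the wait for treatment. Both waits are advanced in one-year steps.

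The programme is built around short intervals. Section 11, Turnaround time, aims for results within 14 days, says that most of the conditions need urgent follow-up, and accepts that some babies will already have symptoms. Appendix A (Test performance and clinical utility) collects age at diagnosis and at treatment start in participants and comparators. A one-year step cannot use differences of weeks or a few months in those data.

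Cost effectiveness is a named secondary outcome, and the model is to report a separate ICER for each of six clusters. Any error would fall mainly on clusters with early-presenting conditions, so it could distort comparisons between clusters as well as the total.

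**Working it through.** The protocol states no ICER, QALY gain or time to diagnosis that rests on the cycle length, so there is no figure to reproduce. The check asks how long a child appears to stay in the delay state for a given true delay.

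**Inputs.** Cycle length of 12 months with half-cycle correction, from the protocol. True mean delay m of 1 to 60 months, utility loss u of 0.1 to 0.5 in the delay state, and exponential exit: all assumptions. The cohort is taken to start in the delay state, because the protocol does not name Model A's entry state. State values are taken as annual values, not as values per episode of delay.

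**Formula.** For cycle length c and mean delay m, let q = exp(−c/m). Modelled months in the state are:

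- counted at cycle start: c/(1−q)
- counted at cycle end: cq/(1−q)
- with half-cycle correction, the average of the two: c × [½ + q/(1−q)]

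Example for m = 3 and c = 12: q = exp(−4) = 0.0183, and 12 × (0.5 + 0.0187) = 6.2 months.

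| True mean delay (months) | Annual cycle, corrected | Error | Monthly cycle, corrected |
|---|---|---|---|
| 1 | 6.0 | +5.0 (500%) | 1.08 |
| 3 | 6.2 | +3.2 (107%) | 3.03 |
| 6 | 7.9 | +1.9 (31%) | 6.01 |
| 12 | 13.0 | +1.0 (8%) | 12.01 |
| 24 | 24.5 | +0.5 (2%) | 24.0 |
| 60 | 60.2 | +0.2 (under 1%) | 60.0 |

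As m shrinks, q goes to zero and the corrected time goes to 12 × ½ = 6 months. That is the floor. Weekly cycles return 1.0, 3.0, 6.0 and 12.0 for the first four rows.

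**Excess QALY loss per affected child** (undiscounted) = u × error in months / 12:

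- m = 1: 0.1 × 5.0/12 = 0.04, to 0.5 × 5.0/12 = 0.21
- m = 3: 0.1 × 3.22/12 = 0.03, to 0.5 × 3.22/12 = 0.13
- m = 6: 0.02 to 0.08
- m = 12: 0.01 to 0.04
- m = 24: 0.004 to 0.02

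**The same step in Model B.** The formula applies unchanged to the wait between screen diagnosis and treatment. If the true mean wait is 1 month, the model holds the baby as pre-symptomatic for 6.0 months. That postpones the effects of treatment and its costs in the screened arm.

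**The case against.** The strongest reply is that the problem depends on a delay the protocol never gives. Section 3, Macroeconomic considerations, says only that the diagnostic odyssey can be lengthy. The 14-day target is the screening turnaround and says nothing about the comparator, and the age-5 window in Principle C spans years. If standard-of-care delays average a year or more, the annual cycle does little harm. This stands, and it limits the point to conditions diagnosed early without screening.

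Second, part of the benefit of screening enters through the different treatment efficacy in Models A and B, which does not depend on months spent in the delay state. This also stands.

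Third, the model is a draft, and scenario analyses for methodological uncertainty are planned, with discount rates as an example. Cycle length could be added there. But the annual cycle is the stated method, no cycle-length scenario is named, and the deterministic sensitivity analysis varies inputs and not structure. The general promise does not remove the problem.

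A reader might go further in three ways that the documents do not support:

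- **Delay is charged in whole years.** In the set-up above, a 1-month delay becomes 12.0 months only if states are counted at cycle start without correction. The protocol states the correction.
- **The error favours screening.** Overstated delay in Model A would do so taken alone. Model B's treatment step is coarsened on the same cycle and can work the other way.
- **Many life-years are at stake.** One might set deaths over a full cycle against deaths over a one-month delay: at an assumed 10% annual probability, 10% against 1 − 0.9^(1/12) = 0.9%. That treats the rest of the year as free of deaths. The diagnosed child moves to a state with its own mortality, which the protocol does not give. If that is also 10%, the excess is nil. If it is 5%, true first-year deaths are 1 − 0.9^(1/12) × 0.95^(11/12) = 5.4%, and the gap falls from 9.1 to 4.6 points.

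**Conclusion.** The point holds in limited form. An annual cycle with half-cycle correction sets a floor of about six months on the mean delay, in a model meant to value earlier diagnosis. For conditions diagnosed within about six months under standard of care, time in the odyssey state, with its cost and utility loss, is overstated. The excess is about 0.03 to 0.21 QALY per affected child at mean delays of 1 to 3 months. It shrinks to 8% or less of the delay at 12 months or more.

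These sizes rest on assumed delays and utility losses, exponential exit, a cohort that starts in the delay state, and annual state values. If costs and utilities were calibrated per episode of delay, the overstatement would be smaller; the protocol does not say that they are. The net effect on the ICER is not established in either direction. The point concerns a secondary outcome and leaves the primary outcome and the sample size untouched.

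**What to change.** In Models A and B, use monthly (or weekly) cycles for the first years, for example to age 5 to match the window in Principle C, and annual cycles after that. Convert annual probabilities to rates before rescaling them to the shorter cycle. Drive exit from the odyssey state by the comparator group's observed age at diagnosis and treatment start, which Appendix A already plans to collect. Report the all-annual version as a cycle-length scenario, so that its effect on the overall and cluster ICERs can be seen. Model C has only a well state and death, so it can stay annual.

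The cost is some recoding, plus expert input where the literature gives only annual values for early life. Age at diagnosis fixes the end of the delay but not its start, so the date of symptom onset, or a stated proxy for it, is also needed. The model is still being iterated, so the change is cheaper now than after it has been populated with study data.
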